3.3.3 End of treatment visit

End of treatment visit is within 30 days after the last dose of study treatment.

[figure not shown]

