6.2 Visit schedule

All screening tests and evaluations must be completed and reviewed to confirm that patients meet all eligibility criteria within 28 days prior to the first administration of study medication (dosing). Tumor assessments available and performed as part of clinical practice prior to obtaining informed consent and within 28 days prior to treatment start may be used; such evaluations do not need to be repeated for screening.

The Investigator will maintain a screening log to record details of all patients screened and to confirm eligibility or record reasons for screening failure, as applicable.

Visits are organized in programmed cycles of 21 days (if there are no delays in treatment owing to the occurrence of an AE). All visits must occur within \pm 2 working days (\pm 1 working day in day 8 of each cycle) from the scheduled date, unless otherwise noted in the schedule of assessments.

Assessments scheduled for day 1 (before treatment) of all cycles must be performed within 48 hours prior to study treatment administration and day 8 (before treatment) of all cycles must be performed within 24 hours prior to study treatment administration, unless otherwise indicated in the schedule of assessments, to confirm to the patient if treatment can be followed up. If a mandatory procedure described in the protocol falls on a bank holiday and/or weekend, this procedure should be performed on the day before or after the holiday (i.e. within a period of \pm 2 working days). The summary of all study assessments are included in **Appendix 1**.

Day 8 visits can be omitted, at the Investigator's discretion, in those patients that permanently discontinue eribulin treatment and continue with pembrolizumab as single agent.

End of treatment visit (EOT) will be performed within 30 days after last study dose and End of Study Visit (including survival status and post-study anticancer therapy evaluation) will take place 12 months after last study dose in the First Course of pembrolizumab phase treatment (\pm 14 days). Telephone contact is acceptable.

Participants who are eligible for retreatment/crossover with pembrolizumab (as described in Section 5.3.5) may have up to two EOT visits, one after the Initial Treatment Period and one after the Second Course Treatment.

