- The DoR is defined as the time from first documented CR or PR until disease progression or death from any cause, according to RECIST v.1.1. In case of the patient first reaching PR and later CR, the duration of CR will be measured and reported separately, starting from the date when first documented and ending when a progressive disease is diagnosed, or the patient dies.

Patients without PD or death will be censored and patients who have not documented neither CR nor PR response will be considered as not available in the Kaplan Meier analysis.

Number of events, median survival time, 95% CI of median and survival curves calculated with Kaplan Meier analysis will be provided.

Safety:

EudraCT number: 2016-004513-27

- The degree of exposure (dose, duration of treatment, number of patients) will be assessed to determine the degree to which study safety can be assessed. These results will be presented with descriptive statistics (n, NA, mean, standard deviation, median and range).
- Adverse events (AEs) and serious AEs (SAEs) will be classified using the Medical Dictionary for Regulatory Activities (MedDRA). AEs will be presented by preferred term (PT) and by system organ class (SOC). Severity, relationship to study drug (eribulin and pembrolizumab), action taken and outcome will be reported as frequency tables.
- Concomitant medications will be coded to the appropriate Anatomical-Therapeutic-Chemical (ATC) code indicating 1st to 4th levels. The results will be reported by frequency tables.
- Deaths and study discontinuations will be described and assessed. It will be reported by frequency tables.

6.2.2 ***Statistical inference***

A Kaplan-Meier survival analysis will be performed to analyze PFS, OS and DoR. The number of events and the median survival time with corresponding 95% CI will be provided.

1- and 2-year survival rates with corresponding 95%CI will be calculated.

Comparisons using log rank test or model of Cox proportional hazards multivariate analysis will be used if needed, and P values of 0.05 or less will be considered to indicate statistical significance.

6.3 ***Exploratory analysis***

6.3.1 ***Summary statistics***

6.4 ***Subgroup analysis***

Subgroup analysis for CBR, ORR, PFS, OS and DoR will be performed outside the indications of the study protocol. The following variables will be part of this analysis to explore differences between subgroups of subjects:

- Ki67 ranges ($\leq 13\%$ (low), 14-19% (medium), $\geq 20\%$ (high))

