- Frequencies for toxicities related to clinically significant laboratory values will be presented (for 2-5 CTCAE grades).

6.8 ***Statistical model assumptions***

The proportional hazards assumption in the Cox model will be checked.

6.9 ***Transformation of expected variables***

- The CBR is defined as the proportion of subjects who have best overall response of CR, PR or SD (by RECIST v.1.1):

$$\text{CBR} = (\text{CR} + \text{PR} + \text{SD}) / \text{Total of subjects}$$

- The ORR is defined as the proportion of subjects who have best overall response of CR or PR (by RECIST v.1.1):

$$\text{ORR} = (\text{CR} + \text{PR}) / \text{Total of subjects}$$

- The time to progression is defined as the difference between start of study drug (C1D1) and the progression date or death (whichever occurs first) or the last tumor assessment documented.

- The time to death is defined as the difference between start of study drug and the date of death.
- Duration of response (DoR) is defined as the difference between first documented CR or PR and the disease progression date (by RECIST v.1.1) or death.
- Duration of treatment is defined as the difference between the first dose administrated of study drug (eribulin and/or pembrolizumab) and the date of EOT visit. If no date of EOT is available, the last administration of study drug will be used.

6.10 *Handling of missing data*

There is no planned procedure of imputation of missing values in other variables. The analysis will be performed with the available data.

6.11 *Description of the softwares to be used for data analysis*

Statistical programming and analyses will be performed using the R statistical software version 3.1.3.

6.12 *Interim analysis protocol*

No interim analysis is planned.

6.13 *List of tables and figures*

The tables below are an approximated list of the tables and figures that will be shown in the statistical analysis. They will be able to modify as required.

List of tables:

Descriptive statistics for the age at the informed consent signature

Absolute and relative (%) frequencies for the race

Absolute and relative (%) frequencies for significant disease and surgical intervention (registered in medical history).

Absolute and relative (%) frequencies for toxic habits

Descriptive statistics for number of relapses

Absolute and relative (%) frequencies for hormonal receptors (ER, PR) and HER2 status

Descriptive statistics for Ki67

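### SAP 6.9 ends duration of treatment at the EOT visit for some patients and at the last dose for others, so the descriptive duration table mixes two quantities that can differ by up to 30 days for identical dosing

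*SAP*

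**What the plan says.** SAP 6.9 (Transformation of expected variables) starts duration of treatment at the first dose of either study drug. It sets the end date, with a fallback, as "the date of EOT visit. If no date of EOT is available, the last administration of study drug will be used".

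The EOT visit is not the day of the last dose. Protocol 3.3.3 states: "End of treatment visit is within 30 days after the last dose of study treatment". Protocol 6.2 and Appendix 1 give the same window, and Protocol 3.3 places the visit in the post-treatment phase. Protocol 6.2 adds that patients eligible for retreatment "may have up to two EOT visits, one after the Initial Treatment Period and one after the Second Course Treatment".

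The variable feeds the safety analysis. SAP 6.2.1 says: "The degree of exposure (dose, duration of treatment, number of patients) will be assessed", with the purpose of finding how far study safety can be judged. The table list in SAP 6.13 has one descriptive table for duration of treatment. No version based on the last dose is planned for all patients.

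**The concern.** The rule pools two quantities under one name. With an EOT date, the value is time to last dose plus the wait until the visit. Without one, it is time to last dose. Part of the spread in the table then reflects visit attendance and scheduling, not dosing.

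Two further gaps follow from the same definition.

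- A retreated patient can have two EOT visits, and SAP 6.9 assumes one. Taking the second counts the interval between courses as treatment. Taking the first leaves out the second course.
- The definition gives one duration spanning both drugs. Protocol 3.1 lets each drug be stopped for toxicity independently of the other, and lets eribulin continue alone after 35 pembrolizumab doses. SAP 6.2.1 tabulates adverse events by relationship to each drug, so drug-attributed events would be read beside a duration that may fit neither drug.

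At stake is the reading of one of the three named components of exposure. No efficacy result uses it.

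**Working it through.** The plan states no figure that depends on this definition, so there is nothing to reproduce first. The check is date arithmetic.

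**Inputs**
- End date: EOT visit, or last administration if there is no EOT date (SAP 6.9).
- Gap g from last dose to EOT: 0 to 30 days (Protocol 3.3.3, 6.2).
- Cycle of 21 days, with eribulin on days 1 and 8 and pembrolizumab on day 1 (Protocol synopsis; SAP synopsis).
- Share m of patients without an EOT date, and the mean gap: not given in the documents, so both are assumptions.

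**Step 1. Patient level.** With an EOT date, SAP duration = time to last dose + g. Without one, SAP duration = time to last dose. The difference for identical dosing is g, which is 0 to 30 days.

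**Step 2. Relative size at the maximum.** If the last dose is on day 1 of cycle k with no delays, time to last dose = 21 × (k − 1) days. The excess is 30 divided by that.

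| Last dose | Time to last dose | SAP value at g = 30 | Excess |
|---|---|---|---|
| Cycle 3 day 1 | 21 × 2 = 42 | 72 | 30/42 = 71% |
| Cycle 6 day 1 | 21 × 5 = 105 | 135 | 30/105 = 29% |
| Cycle 12 day 1 | 21 × 11 = 231 | 261 | 30/231 = 13% |
| Cycle 35 day 1 | 21 × 34 = 714 | 744 | 30/714 = 4% |

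**Step 3. Average effect relative to last dose.** Mean excess = (1 − m) × mean gap.

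| Assumed m | Mean gap 7 days | 15 days | 30 days |
|---|---|---|---|
| 0 | 7 | 15 | 30 |
| 10% | 6.3 | 13.5 | 27 |
| 30% | 4.9 | 10.5 | 21 |

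**Step 4. A different reference point.** Suppose exposure is credited to the end of the last 21-day cycle. That end is 21 days after a day 1 dose and 14 days after a day 8 dose.
- Last dose on day 1: error = g − 21, from −21 to +9 days.
- Last dose on day 8: error = g − 14, from −14 to +16 days.

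The sign is open under this reference. The mixed end dates remain, because a patient without an EOT date is still treated as g = 0.

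**Step 5. Retreated patients.** If the second EOT is used, the excess also includes the whole interval between courses. The documents set no upper limit on that interval, so the 30-day bound does not hold for these patients.

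**The case against.** The strongest reply is that nothing in the documents says exposure ends on the day of the last infusion. Treatment is given in 21-day cycles, and Protocol 7.2 collects non-serious and unrelated serious events until 30 days after the last administration. A duration running to EOT therefore has some link to the period in which safety is observed. That stands against calling the figure simply too high. A reader might infer that exposure is overstated throughout; the documents support this only with the last dose as reference, and Step 4 shows the error can be negative otherwise. It does not justify using two end dates in one table.

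A reader might also divide 30 days by the 4.1-month eribulin median PFS quoted in Protocol 1.3.3 and report about 24%. That sets a maximum gap against another trial's PFS on eribulin alone. PFS is not treatment time here, since treatment may continue past RECIST progression or stop before it.

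It is tempting to add that patients who die early are the ones lacking an EOT date, so the distortion is differential. That is plausible, but the documents give no missing-EOT rate or pattern.

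On retreatment, the SAP may simply predate the second course: its synopsis specifies no maximum treatment duration and a last visit in August 2019, while the protocol has the 35-treatment limit and December 2020. The conditions for retreatment are also narrow. Both remarks explain the gap and limit how many patients it touches; neither closes it.

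Finally, dose has its own table, and the SAP calls its table list approximate. That makes the split by drug more of an improvement than a correction.

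**Conclusion.** The point holds, at minor severity. For identical dosing in a single course, the recorded duration can differ by up to 30 days according to whether an EOT date exists. Relative to the last dose, the EOT-based value is 0 to 30 days too long; relative to the end of the last cycle, the error has no fixed sign. The percentages assume the full 30-day gap and no dosing delays, so they are maxima for patients stopping at those cycles, not expected values. No average can be stated without assuming a mean gap and a missing-EOT rate. For retreated patients the end date is undefined.

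A reader might infer that efficacy results are touched. They are not: CBR, PFS, OS, ORR, DoR and the primary decision rule do not use this variable, and with a single arm there is no between-arm comparison to distort.

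**What to change.** In SAP 6.9, replace the two end dates with one convention anchored to the last administration and applied to every patient. One example is last minus first administration plus 1 day. Another single stated convention would also serve, such as one crediting the final cycle; the plus-1-day version gives 1 day to a patient who received one dose, so the choice should be stated openly.

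Report the duration separately for pembrolizumab and eribulin, and separately for first and second course, so that the off-treatment interval is excluded and no choice between two EOT visits is needed.

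The cost is one SAP definition and a few more rows in one table. Protocol 5.7 already has administered doses recorded in the CRF, and the SAP's own fallback uses the last administration date. The downside is that reported durations become somewhat shorter: under the example convention, a single-course patient with an EOT date loses g days and gains 1, and a patient without one gains 1.

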8 STATISTICAL CONSIDERATIONS AND STATISTICAL ANALYSIS PLAN

8.1 Determination of sample size

A sample size of 44 evaluable patients will be accrued, with an exact single-stage phase II design. The primary endpoint for this study is the CBR. CBR will be evaluated according to the RECIST criteria v.1.1. The CBR of MK3475 (pembrolizumab) in combination with eribulin will be assessed with the exact binomial test. In designing the trial, a CBR of 30% is deemed to be unacceptable in this patient population [16]. In contrast, a CBR of 50% would be considered to be successful. At least 17 patients with clinical benefit among 39 patients will be adequate to justify the investigation of this strategy in further clinical trials. Considering a drop-out rate of 10%, a sample size of 44 patients will be needed to attain 80% power at nominal level of one-sided alpha of 0.05.

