8.4 Missing data management

Study variables could be missing for patients who withdrawn from the trial or for specific visits. We will report reasons for withdrawal. Patient with missing in binary outcomes will be considered as non-responders. The analysis of timed endpoints are based on a Kaplan-Meier methods, therefore, not affected by patient withdrawals (as they are censored) provided that dropping out is unrelated to prognosis. The other variables will be managed with simple imputations methods (last observation carried forward). The effect that any missing data might have on results will be assessed via sensitivity analysis of study sets.

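### Protocol 8.4 and SAP 6.10 conflict on missing descriptive data, and the SAP leaves the CBR/ORR denominator open by omitting the protocol's non-responder rule

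*SAP*

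**What the plan says.** Protocol 8.4 has three rules. For binary outcomes: "Patient with missing in binary outcomes will be considered as non-responders". Time-to-event endpoints are analysed by Kaplan-Meier with withdrawals censored. For everything else: "The other variables will be managed with simple imputations methods (last observation carried forward".

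SAP 6.10 has one short statement: "There is no planned procedure of imputation of missing values in other variables. The analysis will be performed with the available data". In the readable text of that section nothing comes before it, so the word for the remaining variables has no stated counterpart. The non-responder rule appears nowhere in the readable SAP.

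On the denominator, SAP 6.1 bases the primary analysis on the full analysis set, which SAP section 5 defines by eligibility and at least one drug exposure, with no evaluability condition. SAP 6.1.1 divides by all patients in the analysis set, and SAP 6.9 does likewise for CBR and ORR.

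On the decision rule, protocol 8.1 and SAP 4.5 both state: "At least 17 patients with clinical benefit among 39 patients will be adequate". Both then add: "Considering a drop-out rate of 10%, a sample size of 44 patients will be needed". Protocol 8.2.7 and SAP 6.1.2 repeat the 17-of-39 threshold as the consequence of requiring a one-sided exact p-value of at most 0.05. Neither document gives a threshold for 44.

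**The concern.** There are two problems of different weight.

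The first is a plain contradiction. For laboratory values over time (the evolution tables in SAP 6.7), the protocol imputes and the SAP does not. Carrying a value past the point where a patient stopped being measured can hide later deterioration, so the choice affects what a reader sees.

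The second is a gap in the rule that protects the primary endpoint. A programmer working from the SAP alone finds no explicit instruction for a treated patient whose response status is unknown. Such patients are foreseeable. With scans every 9 weeks, the 24-week point falls between the week-18 and week-27 scans, so a patient lost after week 18 has undetermined stable-disease status. Patients without an assessment have often progressed or stopped early, and leaving them out would raise CBR and ORR. The wording on available data, next to a threshold expressed out of 39, could be taken as permission to leave them out.

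**Working it through.** **Inputs.** Null CBR 0.30 ("In designing the trial, a CBR of 30% is deemed to be unacceptable in this patient population"), target CBR 0.50 ("In contrast, a CBR of 50% would be considered to be successful"), and "80% power at nominal level of one-sided alpha of 0.05"; rule of at least 17 of 39; 10% drop-out; 44 enrolled. All are in protocol 8.1 and SAP 4.5. The number of patients without a response assessment is not given, so it is varied below. Five corresponds to 44 − 39.

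**Step 1: reproduce the design.** With X binomial(n, p):
- Type I error: P(X ≥ 17 | n = 39, p = 0.30) = 0.04998.
- Power: P(X ≥ 17 | n = 39, p = 0.50) = 0.8316.
- Drop-out: 39 / (1 − 0.10) = 43.3, rounded up to 44.

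The stated sample size and alpha reproduce. Power exceeds 80% because the exact test is discrete.

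**Step 2: threshold if all 44 are in the denominator.** P(X ≥ 18 | 44, 0.30) = 0.0812 and P(X ≥ 19 | 44, 0.30) = 0.0437, so the critical value is 19. Applying 17 to 44 patients would give a type I error of P(X ≥ 17 | 44, 0.30) = 0.1394.

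**Step 3: compare the two denominators.** With m of 44 unassessed, the non-responder rule always needs 19 benefits. An available-case analysis needs the smallest r with P(X ≥ r | 44 − m, 0.30) ≤ 0.05. A conclusion reverses for counts from r to 18. The last two columns give the probability of such a count when 44 − m patients are assessed and the true CBR among them is 50% or 30%.

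| Unassessed (m) | Available-case n | Available-case threshold | Counts that reverse | Probability at 50% | Probability at 30% |
|---|---|---|---|---|---|
| 1 | 43 | 19 | none | 0 | 0 |
| 2 | 42 | 19 | none | 0 | 0 |
| 3 | 41 | 18 | 18 | 9.2% | 2.1% |
| 4 | 40 | 18 | 18 | 10.3% | 1.7% |
| 5 | 39 | 17 | 17, 18 | 20.6% | 3.9% |
| 6 | 38 | 17 | 17, 18 | 22.7% | 3.1% |

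For m = 5 the p-values are:
- 17 benefits: 17/39, p = 0.04998; 17/44, p = 0.139.
- 18 benefits: 18/39, p = 0.024; 18/44, p = 0.081.

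In that case, at 50% among assessed patients, the chance of a positive trial is 83.2% with 39 in the denominator and 62.5% with 44. The difference of about 21 percentage points is the reversal probability in the table.

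**Step 4: set the missing-data rules side by side.**

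| Type of variable | Protocol 8.4 | SAP |
|---|---|---|
| Binary (CBR, ORR) | missing = non-response | no explicit rule; denominator is the analysis set |
| Time-to-event | Kaplan-Meier with censoring | Kaplan-Meier with censoring |
| Remaining variables | last observation carried forward | no imputation, available data |

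Only the last row is a direct conflict. The first is an omission.

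**The case against.** A reader might infer that the primary test reverses according to which document is followed. The documents do not support that, for four reasons.
- SAP 6.10 limits its no-imputation statement to remaining variables, much as protocol 8.4 does after dealing with binary and timed outcomes. It does not say that binary outcomes are analysed on available cases.
- SAP 6.1, 6.1.1 and 6.9 keep every patient of the analysis set in the denominator. A treated patient with no scan cannot enter the numerator, so the result equals non-responder imputation.
- The formal criterion in both documents is the p-value. Applied to 44 patients, it leads to 19 without further wording.
- The 17-of-39 rule is in both documents, so it is not a difference between them.

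The reversal also requires at least three unassessed patients and a count on the boundary. A drop-out may still have had a scan, so the planned 10% need not all be unassessed.

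Two further inferences should be resisted. Last observation carried forward does not apply to every non-binary variable, because protocol 8.4 censors the timed endpoints. Nor would it distort ECOG over time, since the SAP tabulates ECOG only at baseline. SAP 6.7 also tabulates laboratory toxicities by CTCAE grade, so deterioration would not be judged from the evolution tables alone.

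All of this stands. It does not remove the conflict on descriptive variables. It also does not remove the ambiguity: a design that inflates 39 to 44 for drop-out makes most sense if drop-outs leave the denominator. Protocol 8.1 describes the 44 as evaluable, and the SAP's sentence on available data carries no qualification.

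**Conclusion.** The point holds in two parts. First, protocol 8.4 and SAP 6.10 cannot both be followed for variables outside the binary and timed endpoints; the consequence is confined to descriptive output, chiefly the laboratory evolution tables. Second, the SAP omits the non-responder rule for CBR and ORR. Its stated denominator gives the same answer, so this is a gap in clarity and not a demonstrated contradiction, but an available-case denominator is not ruled out.

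If that reading were taken, the size depends on an assumed number of unassessed patients: nothing with one or two, one boundary count with three or four, and 17 or 18 benefits with five. With five, discordant conclusions would arise with probability 20.6% at a true CBR of 50% among assessed patients and 3.9% at 30%. That is enough to justify settling the wording before the analysis is run.

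**What to change.** 1. **Protocol 8.4:** delete last observation carried forward, so that both documents use observed values for descriptive variables.
2. **SAP 6.10:** state that patients with missing CBR or ORR status, overall and in the PD-L1-positive set, count as non-responders and stay in the denominator of the analysis set. Report the available-case result as a sensitivity analysis only.
3. **Protocol 8.1 and 8.2.7, SAP 4.5 and 6.1.2:** replace 17 of 39 as the success threshold with the exact critical value for the number in the full analysis set, which is 19 if N = 44. Keep 17 of 39 only as the basis of the sample-size calculation.

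The cost is a few sentences in the SAP and a minor protocol amendment; no data collection or sample size changes. The reported CBR is not lowered relative to the SAP's own denominator. What becomes explicit is the power: 85.4% at a true CBR of 50% if all 44 are assessed, and 62.5% if five are not and the 50% applies only to those assessed. That loss already follows from the protocol's non-responder rule.
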